Subjects will receive TMZ chemotherapy as part of the trimodal therapy phase concurrently with radiation and TTF therapy. This will be administered orally by the subjects at a dose of 75mg/m² (of their body surface area) daily during radiation therapy (typically for 42 consecutive days including on weekends, up to 49 days is acceptable; to Day 49 + 7 days). Subjects will then discontinue the chemotherapy and have a 4-week break after radiation prior to resuming TMZ adjuvant therapy concurrent with TTF therapy alone. Doses will then be administered for 5 consecutive days out of a 28-day cycle. For the first cycle of adjuvant therapy, subjects will be dosed at 150mg/m²/day for 5 days out of 28 days in the first cycle, and increased if tolerated to 200mg/m²/day and continue that dose until the end of chemotherapy. The standard requirement is for 6 cycles of adjuvant treatment post-radiation but this may be extended per the judgment of the subject's treating clinician to no more than 12 cycles of adjuvant TMZ therapy. Please see package insert for full details. Expected and potential treatment-related acute adverse effects include: Nausea, fatigue, constipation, liver toxicity, myelosuppression resulting in thrombocytopenia, leukopenia (or neutropenia), anemia, or pancytopenia.

Initiation of PJP prophylaxis is recommended but each site will be given discretion to follow their institutional protocols.

Dose modifications during Trimodal therapy phase

ANC $\geq 500/\text{mm}^3$ but $< 1,500/\text{mm}^3$ **or** platelet count $\geq 10,000/\text{mm}^3$ but $< 100,000/\text{mm}^3$ **or** grade 2 nonhematologic toxicity (excludes alopecia, nausea/vomiting): Interrupt therapy

ANC $< 500/\text{mm}^3$ **or** platelet count $< 10,000/\text{mm}^3$ **or** grade 3/4 nonhematologic toxicity (excludes alopecia, nausea/vomiting): Discontinue therapy

Dose modifications during adjuvant therapy phase (concurrent with TTFields therapy only)

ANC $< 1,000/\text{mm}^3$, platelet count $< 50,000/\text{mm}^3$, or grade 3 nonhematologic toxicity (excludes alopecia, nausea/vomiting) during previous cycle: Decrease dose by 1 dose level (by $50 \text{ mg/m}^2/\text{day}$ for 5 days), unless dose has already been lowered to $100 \text{ mg/m}^2/\text{day}$, then discontinue therapy.

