7. SUBJECT ASSESSMENTS FOR SAFETY AND EFFICACY

The study procedure calendar for this study is provided in **Appendix 3**.

a) Evaluation of Safety and Tolerability**Dose Limiting Toxicity**

Dose limiting toxicities (DLTs) are defined as any severe or life-threatening treatment-related toxicity that precludes the use of a specified dose of any of the study treatments (TTFields, temozolomide, radiation) including continued use of Optune TTFields device at the standard treatment levels and schedule set out by prior studies. This study will prioritize preserving the standard of care for glioblastoma using approved dosing and radiation of temozolomide and radiation.

Toxicities will be graded according to the CTCAE (Version 5.0) scale. If multiple toxicities are seen, the presence of DLT should be based on the most severe toxicity experienced. Dose-limiting toxicities will be defined as any of the following events which occur during the experimental trimodal therapy with TTFields is added concurrently to radiation and temozolomide therapy or during the 8 weeks after RT is completed, and are considered by the investigator to be attributable to TTFields or the combination of TTFields with radiation and/or temozolomide:

- Any Grade > 3 thrombocytopenia, and Grade 4 anemia and neutropenia.
- Any nonhematologic Grade > 3 toxicity (including nausea, vomiting, or diarrhea), excluding alopecia.

- Any Grade 3-4 radiation-induced skin changes that persist for greater than 7 days and does not improve with management recommendations as outlined in toxicity management.
- Any adverse effect deemed by the investigator, patient's primary neuro-oncologist, or radiation oncologist to be life threatening in nature.

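### Section 7a gives two conflicting rules for a patient with several toxicities, and under one of them a worse but non-qualifying event can mask a qualifying Grade 3 skin DLT

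*Combined protocol and SAP*

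**What the plan says.** The rules stand in Section 7a, under Dose Limiting Toxicity.

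- For a patient with more than one toxicity: "If multiple toxicities are seen, the presence of DLT should be based on the most severe toxicity experienced".
- The sentence that follows introduces the list: "Dose-limiting toxicities will be defined as any of the following events which occur during the experimental trimodal therapy", or in the 8 weeks after radiotherapy. Listed events must also be "considered by the investigator to be attributable to TTFields or the combination of TTFields with radiation and/or temozolomide".
- Blood counts: "Any Grade > 3 thrombocytopenia, and Grade 4 anemia and neutropenia".
- Other toxicity: "Any nonhematologic Grade > 3 toxicity (including nausea, vomiting, or diarrhea), excluding alopecia".
- Skin: "Any Grade 3-4 radiation-induced skin changes that persist for greater than 7 days", with the further condition that they do not improve under the recommended management.
- A fourth item covers any effect judged life threatening by the investigator or treating specialist.

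The same section opens with a broader definition: serious treatment-related toxicity that prevents any of the three study treatments being given at its specified dose.

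Section 6 (Safety Lead-ins) halts the study at 2 or more patients with a DLT among 6, and at 5 or more among 15. The DLT rate is a primary endpoint. Section 8 summarises it by counts and percentages of patients, overall and by event type.

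**The concern.** A most-severe rule is harmless when criteria rise with grade, because the worst event is then the one most likely to qualify. Here they do not. Grade 3 skin changes can qualify, while thrombocytopenia and other non-hematologic events need more than Grade 3 as printed. Leukopenia is not named in the list, and every listed item carries the attribution test. The worst event a patient has may therefore fail the criteria while a lesser one meets them.

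The ingredients are foreseeable. The synopsis names skin toxicity as the expected toxicity. Every patient is to receive temozolomide, whose expected effects in Section 6 include "myelosuppression resulting in thrombocytopenia, leukopenia (or neutropenia), anemia, or pancytopenia".

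At stake are a primary endpoint and both interim decisions. With two sites, and the first lead-in assessed by investigators, identical patients could also be classified differently depending on which sentence the assessor follows.

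**Working it through.** The plan states no figure on this point, so the check has two parts: reading the sentences against each other, and finding how much a misclassification could matter.

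**Reading**

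Take two patients, each with a Grade 3 skin event that meets every part of the skin item and the attribution test. The second also has Grade 4 leukopenia attributed to temozolomide alone.

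| Patient | Most-severe sentence | Any-event sentence |
|---|---|---|
| Skin event only | DLT | DLT |
| Skin event plus leukopenia | judged on the leukopenia; fails attribution; no DLT | DLT |

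The disagreement runs one way. If the most severe event qualifies, the any-event rule counts the patient too. The most-severe count can therefore only equal or fall below the any-event count.

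**Boundary**

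One masked patient turns 2/6 (halt) into 1/6 (proceed), or 5/15 (halt) into 4/15 (proceed).

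**Probability**

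Let p be the true DLT rate under the any-event rule and m the share of DLT patients who are masked. The counted rate is p(1 − m). The documents give neither p nor m, so both are assumptions. The calculation treats every DLT as equally maskable, which is an upper-end simplification.

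For the first look, P(at least 2 of 6) = 1 − (1 − q)^6 − 6q(1 − q)^5, with q = p(1 − m).

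- Section 8 expects 5% severe skin irritation. This is not a DLT rate, but it is the nearest planning figure.
- With p = 0.05 and m = 0: 1 − 0.735 − 0.232 = 0.033.
- With p = 0.05 and m = 0.20, q = 0.05 × 0.80 = 0.04: 1 − 0.783 − 0.196 = 0.022 (rounded from unrounded terms).
- In patients: 0.05 × 30 = 1.5 expected events, of which 20% is 0.3 of a patient in the whole trial.

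For either look, the probability of halting is 1 − Σ (a = 0, 1) P(Bin(6, q) = a) × P(Bin(9, q) ≤ 4 − a).

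| p | m | q | At least 2 of 6 | At least 5 of 15 | Halt at either look |
|---|---|---|---|---|---|
| 0.05 | 0 | 0.05 | 0.033 | 0.001 | 0.033 |
| 0.05 | 0.20 | 0.04 | 0.022 | 0.000 | 0.022 |
| 0.20 | 0 | 0.20 | 0.345 | 0.164 | 0.383 |
| 0.20 | 0.20 | 0.16 | 0.247 | 0.078 | 0.267 |
| 0.33 | 0 | 0.33 | 0.642 | 0.585 | 0.746 |
| 0.33 | 0.20 | 0.264 | 0.499 | 0.361 | 0.575 |

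The last two rows require about one patient in three to have a DLT, and all of those DLTs to be of the maskable kind.

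**The case against.** The strongest reply is that the any-event sentence is the operative definition. It follows immediately and introduces the list. Section 6 counts patients in whom a DLT occurs, and Section 8 reports DLTs by event type; neither applies a worst-event filter. The most-severe sentence might be meant only to choose among qualifying events. That is a fair reading and probably the intended one, but no text confirms it: the sentence governs whether a DLT is present and does not limit the toxicities it ranks. What stands is that this is a contradiction. A reader might infer that the protocol has a settled rule that hides skin DLTs; the documents do not support that.

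The second reply is that the masking event may itself count. Under the broader definition, temozolomide toxicity that prevents temozolomide dosing could be a DLT, and Section 6 discontinues temozolomide for an ANC below 500 or platelets below 10,000. This stands for those events, and it exposes a second conflict, between the broad and itemised definitions. It does not cover everything. The temozolomide rules use ANC, platelets and non-hematologic toxicity, so leukopenia alone triggers none of them. The life-threatening item does not rescue the case either, because it carries the same attribution test.

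Third, Section 6 separately makes it a DLT if TTFields cannot be resumed within a month and is discontinued. That catches the most prolonged skin events, but not one that qualifies after 7 days and still allows resumption within the month.

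Finally, masking requires the worse event to be judged unrelated to TTFields in a patient receiving all three treatments, and Section 7 classes even a possible link as related. That should make such patients uncommon.

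**Conclusion.** The contradiction is real: two adjacent sentences classify the same patient differently, and nothing in Section 8 settles it. Any error from following the first sentence is toward under-counting and proceeding. With such small thresholds, one patient can reverse an interim decision.

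The likely size is small. Near the plan's own 5% figure, an assumed 20% masked share changes the chance of halting at the first look by about one percentage point (3.3% to 2.2%). A reader might infer from the 33% rows that the stopping rules are badly weakened. That needs a high assumed DLT rate made up entirely of maskable events, and the documents support neither assumption. This is worth correcting because the ambiguity sits in a primary endpoint and is easily removed, not because a large bias has been shown.

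**What to change.** Reconcile the two sentences in Section 7a, and the broad and itemised definitions in the same section. For the DLT endpoint and the 6- and 15-patient counts, state that each toxicity is judged separately; that a patient is counted once as having a DLT if any one toxicity meets any listed criterion; and that severity serves only to choose which qualifying event is reported. This follows the protocol's own any-event definition and suits the by-type reporting in Section 8.

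Section 7a also ties a DLT to stopping the subject's treatment. How the reconciled definition bears on that consequence is for the sponsor to settle; no clinical rule is proposed here.

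The cost is a short text amendment. No new data are needed, since all events of Grade 3 and above are already recorded with attribution. The counted DLT rate may be slightly less favourable.

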 - a. If the skin beneath the Transducer Arrays is inflamed, a high potency topical steroid (e.g. clobetasol) may be prescribed to the patient. The patient or caregiver should apply the ointment after removing the arrays and cleaning the scalp with baby oil and medical alcohol. The ointment should be left on the scalp for at least 30 minutes prior to washing the skin with a mild shampoo and applying a new set of arrays.
 - b. At each array replacement, the new set of arrays should be shifted by approximately 2 cm compared to the previous layout so that the array discs are placed between the areas of skin irritation. At the next array replacement, the arrays should be shifted back to their original location.
 - c. If the dermis is breached (skin erosions, ulcers, open sores, punctate lesions, etc.) an antibiotic ointment (e.g. mupirocin) should be prescribed and used in place of the steroid ointment. Any evidence of infection should result in bacterial cultures being taken. During radiotherapy, a break from the Optune array is mandatory if there is ulceration or open sores.
8. Expected and potential treatment-related acute adverse effects include: Localized skin toxicity, anxiety, headaches, fatigue, insomnia, seizures.

Dose modifications during TTField therapy (applies to *all phases of therapy*--trimodal therapy, adjuvant therapy, or maintenance therapy, including for the safety lead-ins):

Grade 3-4 non-hematologic toxicity (skin toxicity, neurologic symptom, etc): reduce device usage schedule to 50% or 1 week on, 1 week off to allow for recovery. If toxicity remains grade 3 or above for 1 month after reduced usage, then discontinue therapy. If non-hematologic toxicity moves to grade 2 or below, titrate up as soon as able to tolerate, per investigator discretion. If skin toxicity improves to grade 2 or below in the 1-month period, the original TTF usage can be resumed per investigator discretion. If TTF therapy could not be resumed in the 1-month period and has to be discontinued then it would be considered DLT for Optune use.

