In the event of a dose-limiting toxicity, the subject will be discontinued from treatment and followed for toxicity assessment and management and a joint decision will be made by the investigator and sponsor whether to adjust the dose or schedule for other subjects or permanently close the study for safety. In the event that more than 33% of subjects experience a DLT, the study cannot continue unless a modification is made to the level of the particular treatment to which that adverse event is definitely attributable. As preliminary safety stops, the study will include two safety lead-ins receiving TTFields with concurrent chemoradiation. These initial 6 and then 15 subjects will undergo interim analyses after completion of chemoradiation to determine if the expanded cohorts should be permitted enrollment as planned or if a dose reduction in TTFields of 50% of the scheduled use is warranted for safety.

Subjects will continue to receive study treatment until confirmed tumor progression, unacceptable toxicity, or other discontinuation criteria as described; subjects MUST discontinue investigational product (and non-investigational product at the discretion of the investigator) if they meet criteria for removal from study therapy as referenced in that section.

Toxicity related to TTFields treatment: Treatment-related adverse events (TRAEs) and severe treatment-related adverse events (STRAEs) will be assessed in the following ways.

- Patients will be evaluated by a neuro-oncologist or radiation oncologist for potential skin toxicity from TTFields therapy. Routine skin care recommendations will be provided, including use clobetasol cream prior to electrode placement and adjusting array placement to avoid continued site irritation. If there are concerns by investigator, the subject will be referred to a dermatologist for specialized evaluation. Neurological and general physical evaluations as well as laboratory assessments will also be conducted by a neuro-oncologist or radiation oncologist to identify other potential toxicities.
- In addition to clinic visits and interventions, Patients will also be supported by a technician from Novocure for device troubleshooting and compliance checks.
- All other adverse effects, either mild, or serious, will be triaged by a physician in coordination with the primary investigators of the study.

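### For a non-skin Grade 4 nonhematologic toxicity attributed to TTFields in the DLT window, Section 7a stops treatment while Section 6 orders a half schedule with re-titration

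*Combined protocol and SAP*

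**What the plan says.** Section 7a, *Dose Limiting Toxicity*, lists the events that are DLTs when the investigator attributes them to TTFields or to its combination with the other modalities. Section 6, *Safety Lead-ins*, sets the window from the start of TTFields to 8 weeks after radiotherapy (RT) ends. The second bullet of the list is "Any nonhematologic Grade > 3 toxicity (including nausea, vomiting, or diarrhea), excluding alopecia". The third has its own condition: "Any Grade 3-4 radiation-induced skin changes that persist for greater than 7 days and does not improve with management recommendations". After the list comes the action: "In the event of a dose-limiting toxicity, the subject will be discontinued from treatment and followed for toxicity assessment and management". The rest of that sentence concerns changes for other subjects, not for the affected one.

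Section 6, *Dose modifications during TTField therapy*, applies to trimodal therapy, "adjuvant therapy, or maintenance therapy, including for the safety lead-ins". For Grade 3-4 non-hematologic toxicity, with skin and neurologic symptoms as examples, the instruction is "reduce device usage schedule to 50% or 1 week on, 1 week off to allow for recovery". It continues: "If toxicity remains grade 3 or above for 1 month after reduced usage, then discontinue therapy". It then adds: "If non-hematologic toxicity moves to grade 2 or below, titrate up as soon as able to tolerate, per investigator discretion". It closes by saying that if TTFields could not be resumed within the month and "has to be discontinued then it would be considered DLT for Optune use".

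Section 6, *Criteria for Removal from Study Therapy*, item 2, requires immediate cessation for a serious event that the treating physician considers life threatening and that is definitely related to the device.

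**The concern.** A Grade 4 neurologic event in week 3, rated probably related to TTFields, meets both rules on its first day. Section 7a takes the patient off treatment. Section 6 keeps the patient on the device at half schedule and moves usage back up once the event is Grade 2 or lower. Both are written as instructions, and nothing ranks one above the other.

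The trial runs at two institutions, with three first lead-in patients expected from each. Both sites could follow the protocol and handle the same severe event in opposite ways. Safety of concurrent TTFields is the primary objective, so this instruction should have one reading. Duration of TTFields use, a secondary endpoint, would also depend on which section a site applied.

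**Working it through.** **1. Do the two rules cover the same event?**

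| | Section 7a | Section 6 dose modifications |
|---|---|---|
| Grade, nonhematologic | above 3, so 4 or 5 | 3-4 |
| Period | DLT window | all phases, lead-ins named |
| Recovery condition | none in the second bullet | Grade 2 or below leads to up-titration |
| Action on the patient | discontinue | 50% schedule; discontinue only after 1 month at Grade 3 or above |

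They overlap at Grade 4, in the window, when the event is attributed to TTFields or the combination. Discontinue cannot be read as pause: the temozolomide rules in Section 6 use interrupt and discontinue as separate actions, and the TTField rule contrasts reducing with discontinuing.

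**2. Does another provision decide?** Removal item 2 needs three things: serious, deemed life threatening, and definitely related. The protocol's own grading scale describes Grade 4 as life threatening, so the gap is mainly attribution. The attribution table in Section 7 has three related categories (possible, probable, definite), and only one of the three triggers item 2. Definite also requires that other therapeutic interventions cannot reasonably explain the event. Section 6 lists six expected TTFields effects, five of them non-skin: anxiety, headaches, fatigue, insomnia and seizures. Three of those five (headache, fatigue, seizure) are also on its RT list. A rating below definite is therefore foreseeable, although the documents do not show that these effects reach Grade 4.

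**3. Skin.** The third bullet of Section 7a names Grade 3-4 radiation-induced changes and requires more than 7 days without improvement. *Radiation therapy without interruptions* already imposes at least a 1-week break from TTFields for Grade 3-4 skin toxicity during RT, and the skin-care guidelines require a break for ulceration or open sores. If the third bullet governs Grade 4 radiation-induced changes, little conflict remains. If the second does, the open question is resumption versus discontinuation.

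**4. Size per affected patient, 28 days from a non-skin event,** at the minimum average use of 18 h/day:
- Section 7a, no re-challenge: 0 device-days.
- Section 6, half schedule kept throughout: 2 weeks × 7 = 14 days; 14 × 18 = 252 h.
- Section 6, off week first and full usage from day 8: 28 − 7 = 21 days; 21 × 18 = 378 h.

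The last two are examples, not bounds, since the order of weeks and the pace of titration are not fixed.

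**5. Ceiling beyond 28 days.** Planned TTFields duration is 24 months. For an event on Day 43 with TTFields started on Day 1: 42 / 30.44 = 1.4 months used; 24 − 1.4 = 22.6 months remaining.

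**The case against.** The best reply is that no site is held to the half schedule against its judgement. A patient may stop for intolerable device-attributable events (removal item 2). The investigator may stop for safety, with significant neurological decline named (item 4). Up-titration is discretionary. *Follow-up of Adverse Events* in Section 7 permits re-challenge after a stop, so the two routes can end in the same place. This lowers the practical risk, and it stands to that extent. But these provisions are permissive. They do not say which of two directive sentences governs, and re-challenge follows a stop for selected events, which is not the same as an immediate half schedule.

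A second reply is that the risk the trial expects is skin toxicity, and there the rules nearly fit together. That largely stands. A reader might infer that the conflict reaches the trial's main risk. The documents do not support this, because of the third bullet's 7-day condition and the mandatory breaks. The clear conflict is non-skin, where the *Power Calculation* expects no significant departure from EF-14.

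**Conclusion.** The conflict is real for in-window, non-skin Grade 4 nonhematologic events attributed to TTFields or the combination and not caught by removal item 2. It should be fixed because it is a safety instruction with two opposite readings. The number of patients affected is unknown and may be zero. The only planning rate is 5% severe skin irritation (0.05 × 30 = 1.5 patients), with no Grade 4 share and no non-skin figure. The device-day comparison assumes that treatment in Section 7a includes TTFields, which that sentence does not spell out, and that there is no re-challenge.

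Two stronger readings are not supported. A reader might infer that the 2-of-6 and 5-of-15 stopping counts change. Section 7a counts every listed event, and the closing sentence in Section 6 does not say that its route to a DLT is the only one, so the counts stand on the text. A reader might also take 22.6 months as the expected loss. It is a ceiling: treatment ends at progression, and the background section gives a median progression-free survival of 7.1 months with TTFields plus temozolomide.

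**What to change.** In *Dose modifications during TTField therapy*, limit the 50% and re-titration rule within the DLT window to events that are not DLTs under Section 7a. Add that:

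- an in-window event meeting Section 7a, including any non-skin Grade 4 nonhematologic event attributed to TTFields or the combination, stops TTFields, with restart only as re-challenge under *Follow-up of Adverse Events*;
- the DLT for Optune use described in Section 6 is an additional route to a DLT and does not replace the Section 7a list.

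This follows the rule Section 7a already states. It needs wording in one amendment and no extra patients, visits or procedures. The downside is that a few patients who might have recovered on the half schedule would stop TTFields unless re-challenged. The investigators could also say which bullet governs Grade 4 radiation-induced skin changes, but removing the non-skin conflict does not depend on it.
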